4.4 Early Withdrawal of Subjects

Subjects may withdraw from study participation at any time without any effect on their care at the ACS. Additionally, subjects will be withdrawn early from the study if the investigators are unable to communicate with them or obtain medical records.

5 Study Procedures

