5.2 Follow Up

Every 6 months (+/- 4 weeks), subjects will be contacted and follow up information will be obtained. When possible, these visits will be conducted when the subject has an appointment at the ACS and will be done in person. If the subject is no longer being seen by the ACS, information will be obtained by phone or by searching the subject's medical record. If needed, family or friends as designated by the subject at study enrollment, will be contacted in order to obtain information about the subject outcomes.

If the subject was enrolled utilizing an LAR, the study will be re-explained and assent will be obtained and documented in the source document prior to any study procedures.

Follow up Mini-Cog™ evaluations will only be done if the visit is done in person. See attached Follow-Up Data Collection Form for details regarding what information will be obtained at these visits.

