5.4 Assessments

Mini-Cog™ (used by permission) is a validated screening tool used to detect dementia.⁵

CHA₂DS₂-VASc score is a validated tool for stroke risk stratification.³

HAS-BLED score is a validated schema for risk stratification for bleeding events among anticoagulated patients.¹

Dalhousie University Clinical Frailty Scale is a simplified scale to assess frailty.⁴

Mobility score is a simple noting of patient mobility at each visit- ambulating without assist, ambulating with cane, ambulating with walker, or arrived in wheelchair.

Time in Therapeutic Range (TTR) will be calculated utilizing the Rosendaal method of percentage days in therapeutic range in the past 6 months.

6 Analysis Plan

Compare by decade:

Sex

Living arrangement

Alcohol use

CHA2DS2-VASc score

HAS-BLED score

Dalhousie University Clinical Frailty Scale

Mobility score

TTR for 2 years and best and worse 6 months

Death secondary to anticoagulation

Death secondary to cardiovascular causes

Number of hospitalizations

Major bleeding defined as any bleeding meeting at least one of the following criteria:

- Fatal bleeding
- Symptomatic bleeding in a critical area or organ, such as intracranial, intraspinal, intraocular, retroperitoneal, intraarticular or pericardial or intramuscular with compartment syndrome, and/or
- Bleeding causing a fall in hemoglobin level of 2 g/dl or more, or leading to transfusion of two or more units of whole blood or red cells.²

CNS Bleeds with death, disability, or no disability

Embolic ischemic stroke

Non embolic ischemic stroke

Mechanism unknown ischemic stroke

Hemorrhagic stroke non traumatic

Traumatic intracerebral hemorrhage

Traumatic subdural hemorrhage

Cardiovascular events (non stroke type)

7 Confidentiality

Subject information will be kept in the PBMC Clinical Research office which is locked when unattended. Information entered into a database will be housed on a PBMC shared drive which is password protected. Information about study subjects will be kept confidential and managed according to the requirements of the Health Insurance Portability and Accountability Act of 1996 (HIPAA).

- Protected health information (PHI) which will be collected from subjects in this study include, demographics, medical history, medication list, information related to adverse events, symptoms related to atrial fibrillation and the use of anticoagulants.
- The investigator and his designees will have access to this information.

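### Section 5.2 lets a phone call alone count as follow-up once a subject has left the Anticoagulation Service, so some major bleeds and stroke types may be missed or misclassified

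*Protocol*

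**What the plan says.** Protocol section 5.2 sets the contact schedule: "Every 6 months (+/- 4 weeks), subjects will be contacted and follow up information will be obtained". Visits are in person at the ACS when possible. For a subject who no longer attends, "information will be obtained by phone or by searching the" medical record. A third source is conditional: "If needed, family or friends as designated by the subject at study enrollment, will be contacted". The content of each contact is left to an attachment: "See attached Follow-Up Data Collection Form for details regarding what information will be obtained at these visits". Section 5.3 makes the 24-month visit identical to the others, so the same rule runs to the end of the study.

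Section 5.1 is stricter at enrollment. There, information comes from the subject or caregiver and also from the medical record.

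Section 6 counts a bleed as major if it meets at least one of three criteria. Two are fatal bleeding and symptomatic bleeding at a critical site. The third is "Bleeding causing a fall in hemoglobin level of 2 g/dl or more, or leading to transfusion of two or more units". The same section compares several stroke and intracranial bleeding categories by decade, one of them "Mechanism unknown ischemic stroke". These categories are named but not defined.

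Section 4.4 adds that "subjects will be withdrawn early from the study if the investigators are unable to communicate with them or obtain medical records".

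The SAP takes time in therapeutic range (TTR) as the primary outcome. Death from any cause, stroke and major bleeding are secondary outcomes, and the comparison is across the three age groups.

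**The concern.** The two sources in section 5.2 are joined by *or*. A phone call to someone who has left the ACS completes the contact, and the text gives no order of sources, no duty to obtain the record when an event is reported, and no adjudication.

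Some outcomes in section 6 rest on facts that a subject, relative or friend cannot be relied on to know: the size of a hemoglobin fall, the number of units transfused, whether a stroke was ischemic or hemorrhagic, and whether it was embolic. The protocol itself foresees impaired recall and proxy reporting, since it screens with the Mini-Cog and allows enrollment through a legally authorized representative.

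What is at stake is the comparability of two secondary outcomes across age groups. If the share followed by phone alone differs by decade, part of any difference in major bleeding or stroke type could come from the data source and not from age.

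**Working it through.** **The text side by side**

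- *Source rule.* Enrollment (5.1) requires the record in addition to the interview. Follow-up after leaving the ACS (5.2) accepts either one. The weaker rule applies where outcomes are collected.
- *Major bleeding.* Of the three criteria, only the hemoglobin/transfusion one has a numerical threshold. A fatal or critical-site bleed has none and may be reportable by a subject or relative. The exposed events are therefore bleeds that qualify through the third criterion alone.
- *Stroke.* A stroke reported without its mechanism can be filed as ischemic of unknown mechanism. It then still counts as a stroke in the SAP's secondary outcome, but in the wrong row of the section 6 comparison. Even that row presumes the stroke is known to be ischemic. A hemorrhagic event filed there would also be lost from the critical-site criterion for major bleeding.

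**Size**

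The plan states no sample size, event rate or leaving rate, so it has no figure to reproduce. Every input below is an assumption.

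- L = share of subjects who leave the ACS: 10% to 30%
- q = share of leavers followed by phone only: 50% to 100%
- s = share of true events captured by phone: 0.5 to 0.9
- r = event risk of leavers relative to those who stay: 1 to 3

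Share of all events that occur in leavers: w = L·r / (L·r + 1 − L). Share of all events missed: w·q·(1 − s).

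| Case | L | q | s | r | w | Missed |
|---|---|---|---|---|---|---|
| Low | 0.10 | 0.5 | 0.9 | 1 | 0.100 | 0.100 × 0.5 × 0.1 = 0.5% |
| Middle | 0.20 | 1 | 0.7 | 1 | 0.200 | 0.200 × 0.3 = 6.0% |
| Middle | 0.20 | 1 | 0.7 | 2 | 0.4/1.2 = 0.333 | 0.333 × 0.3 = 10.0% |
| Middle | 0.20 | 1 | 0.7 | 3 | 0.6/1.4 = 0.429 | 0.429 × 0.3 = 12.9% |
| High | 0.30 | 1 | 0.5 | 3 | 0.9/1.6 = 0.5625 | 0.5625 × 0.5 = 28.1% |

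These figures apply one capture rate to every event, which overstates the loss for major bleeding. If, as a further assumption, half of major bleeds qualify only by hemoglobin or transfusion and the rest are fully captured, the high case halves: 0.5625 × 0.5 × 0.5 = 14.1%.

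**Age comparison**

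Take an equal true risk of 10% in two groups, with L = 10% in one and 30% in the other, q = 1, and no false reports.

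- s = 0.9, r = 1: 10 × (1 − 0.10 × 0.1) = 9.9% and 10 × (1 − 0.30 × 0.1) = 9.7%; ratio 0.98.
- s = 0.5, r = 3: w is 0.3/1.2 = 0.25 and 0.5625, so 10 × (1 − 0.25 × 0.5) = 8.75% and 10 × (1 − 0.5625 × 0.5) = 7.19%; ratio 0.82.

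**Direction**

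Let f be the share of event-free, phone-only leavers wrongly counted as events. With r = 1 and q = 1, observed risk = (1 − L)·p + L·[p·s + (1 − p)·f]. Take p = 10% and s = 0.7.

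- L = 20%, f = 0: 0.08 + 0.2 × 0.07 = 9.4%.
- L = 20%, f = 5%: 0.08 + 0.2 × (0.07 + 0.045) = 10.3%.
- f = 5%, L = 10% against 30%: 0.09 + 0.1 × 0.115 = 10.15% and 0.07 + 0.3 × 0.115 = 10.45%; ratio 1.03.

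The sign of the error, overall and between age groups, depends on inputs that the documents do not supply.

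**The case against.** Section 5.2 permits phone-only follow-up but does not prescribe it. Staff may search the record and may contact people the subject has named, and nothing stops them from checking the chart after a reported event. Section 4.4 mentions obtaining records, which suggests that records are expected to be sought. The follow-up form is not in the available text and may ask for hemoglobin, transfusion or the source of the information. All of this stands, and it limits the point to what the protocol text guarantees. It does not remove the point: an optional search is not a rule, and section 4.4 governs withdrawal, not confirmation of events.

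A reader might infer something stronger: that events are under-counted, that this happens in the subjects most likely to have them, and that the oldest group will therefore look safer than it is. The documents do not support that. They give no reasons for leaving the ACS, no leaving rate by age and no event risk among leavers, and unverified reports can also over-count.

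Nor can it be said that every bleed reported by phone fails the definition, since two of the three criteria have no laboratory or transfusion threshold. No imaging requirement for stroke is written either. Finally, section 5.2 does not name the source of outcome data at in-person visits, so a clean split between records for those who stay and recall for those who leave is not established.

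**Conclusion.** The concern holds in limited form. After a subject leaves the ACS, the protocol allows follow-up by phone alone, without record confirmation. Bleeds that are major only by hemoglobin or transfusion, and the type of a stroke, may therefore be missed or misclassified, possibly unequally by age group.

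Neither size nor direction can be determined from the documents. The 0.5% to 28.1% range, and the age ratios of 0.82 to 0.98 without false reports and 1.03 with them, are illustrations that rest wholly on assumed inputs. They show that the effect could be trivial or material, not which it is.

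The point concerns two secondary outcomes. For stroke, it affects the type comparisons in Protocol section 6 more than the SAP's overall stroke outcome. It does not touch TTR. The change is worth making because it is cheap and uses a source the protocol already allows.

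**What to change.** 1. In section 5.2, for subjects no longer seen by the ACS, make the two sources joint: by phone and, where obtainable, by searching the medical record.
2. That edit reaches only subjects who have left, so add a rule for all subjects at every 6-month contact: seek the record for any reported bleed, stroke, hospitalization or death, and classify the event from that record when it is available.
3. Add a field for the source of each event (record, subject, family or friend).
4. In the SAP, list reported but unconfirmed events by decade. Analyze major bleeding and stroke with these events excluded and then included, labelled as lower and upper bounds. Counting every unconfirmed report is an extreme case. The bounds cover reported events only; events never reported are addressed by the record search in step 1.
5. Clarify section 4.4 so that a subject is not withdrawn from the study solely because one of the two sources is unavailable. Its present wording can be read either way.

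The cost is a short protocol edit, a form field, a few SAP sentences and extra chart-search time for existing staff in a study that section 8.1 says is unfunded. Some outside records may not be obtainable. The SAP is written in the past tense; if follow-up is already complete, steps 2 to 4 can still be done retrospectively where records are available.

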5.3 Final Visit

The final visit will be done 24 months (+/- 4 weeks) after the enrollment visit. It will not differ from the other follow up visits in any way.

5.4 Assessments

Mini-Cog™ (used by permission) is a validated screening tool used to detect dementia.⁵

CHA₂DS₂-VASc score is a validated tool for stroke risk stratification.³

HAS-BLED score is a validated schema for risk stratification for bleeding events among anticoagulated patients.¹

Dalhousie University Clinical Frailty Scale is a simplified scale to assess frailty.⁴

Mobility score is a simple noting of patient mobility at each visit- ambulating without assist, ambulating with cane, ambulating with walker, or arrived in wheelchair.

Time in Therapeutic Range (TTR) will be calculated utilizing the Rosendaal method of percentage days in therapeutic range in the past 6 months.

6 Analysis Plan

Compare by decade:

Sex

Living arrangement

Alcohol use

CHA2DS2-VASc score

HAS-BLED score

Dalhousie University Clinical Frailty Scale

Mobility score

TTR for 2 years and best and worse 6 months

Death secondary to anticoagulation

Death secondary to cardiovascular causes

Number of hospitalizations

Major bleeding defined as any bleeding meeting at least one of the following criteria:

- Fatal bleeding
- Symptomatic bleeding in a critical area or organ, such as intracranial, intraspinal, intraocular, retroperitoneal, intraarticular or pericardial or intramuscular with compartment syndrome, and/or
- Bleeding causing a fall in hemoglobin level of 2 g/dl or more, or leading to transfusion of two or more units of whole blood or red cells.²

CNS Bleeds with death, disability, or no disability

Embolic ischemic stroke

Non embolic ischemic stroke

Mechanism unknown ischemic stroke

Hemorrhagic stroke non traumatic

Traumatic intracerebral hemorrhage

Traumatic subdural hemorrhage

Cardiovascular events (non stroke type)

7 Confidentiality

Subject information will be kept in the PBMC Clinical Research office which is locked when unattended. Information entered into a database will be housed on a PBMC shared drive which is password protected. Information about study subjects will be kept confidential and managed according to the requirements of the Health Insurance Portability and Accountability Act of 1996 (HIPAA).

- Protected health information (PHI) which will be collected from subjects in this study include, demographics, medical history, medication list, information related to adverse events, symptoms related to atrial fibrillation and the use of anticoagulants.
- The investigator and his designees will have access to this information.
- The subject has the right to revoke their authorization for use of their PHI at any time. In the event that a subject revokes authorization to collect or use PHI, the investigator, by regulation, retains the ability to use all information collected prior to the revocation of subject authorization.

8 Study Finances

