4.1 Inclusion Criteria

1. Subject must be 70 years of age or older
2. Subject must have electrocardiographically confirmed atrial fibrillation
3. Anticipated regular follow with patient by PBMC Anticoagulation Services
4. Subject (or legally authorized representative) must be willing to provide informed consent

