4.3 Subject Recruitment and Screening

Subjects will be recruited from the PBMC Anticoagulation Services (ACS) department. The medical records used by the ACS will be searched using age ≥ 70 and diagnosis of atrial fibrillation as search criteria. All patients aged 90 years or older who fit the criteria will be approached about participation in the study.

An equal number of patients from the ACS who are aged 80-89 years and, an equal number of patients from the ACS will be enrolled who are aged 70-79 years will be enrolled.

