Official Title: **ATIVO Study – Anticoagulation Therapy in the Very Old**

NCT #: **03103763**

Statistical analysis plan

For the purpose of this study, we attempted to detect differences in outcomes among age groups (70-79, 80-89, and 90+) undergoing anticoagulation therapy at study enrollment and in 6-month intervals for 24 months. Descriptive statistics were used to summarize the demographic (age group, sex, and living arrangement) and clinical characteristics (mobility, alcohol use, CHADS2-VASc, Fragility score, mini Cog, and mobility scale) of patients included in the study, with continuous variables presented as a mean +- standard deviation and categorical variables as frequencies/percentages of the total. The primary outcome of interest was time in therapeutic range (TTR), a percentage of time that a patient's International Normalized Ratio (INR) values were in range over a 6-month period. Secondary outcomes were all-cause mortality, stroke, and major bleeding events. Student t tests and chi-squared tests were conducted to compare data between groups. Statistical significance was set at $P < .05$ with a 95% confidence interval.

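### The total CHA2DS2-VASc score, which counts age, is compared between age decades, so contrasts with the 70-79 group contain a built-in gap of up to 1 point

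*Protocol*

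**What the plan says.** Protocol section 4.1 admits patients from age 70 ("Subject must be 70 years of age or older"). Section 4.3 recruits by decade around the 90-and-over group, with matching numbers at 80-89 and 70-79 ("an equal number of patients from the ACS will be enrolled who are aged 70-79 years"). It gives no target number.

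Section 5.4 introduces the "CHA₂DS₂-VASc score" and says that this "score is a validated tool for stroke risk stratification". Neither document lists its components or point weights. Section 6 places the total score under the instruction "Compare by decade". Sex is a separate item in the same list.

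The SAP aims to "detect differences in outcomes among age groups (70-79, 80-89, and 90" and over). It names the score in its sentence on descriptive statistics, among the clinical characteristics: "mobility, alcohol use, CHADS2-VASc, Fragility score, mini Cog, and mobility scale". A later sentence applies t tests and chi-squared tests to comparisons between groups in general, at the 5% level, without saying which variables are tested. The primary outcome is time in therapeutic range. The secondary outcomes are all-cause mortality, stroke and major bleeding.

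**The concern.** The grouping variable is also part of the measured variable. If patients under 75 receive fewer age points than older patients, the 70-79 group will have a lower mean total than the older groups before any clinical risk factor is counted. A difference in the total would then not show whether the decades differ in clinical stroke risk.

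This matters because CHA2DS2-VASc is the only summary of stroke risk in either analysis list. Heart failure, hypertension, diabetes, prior stroke and vascular disease are not listed separately, and no adjusted analysis is described. A reader asking whether a difference in stroke between decades goes with age or with other disease would look to this score, which already counts age. Protocol section 2 also aims to identify risk factors that impede safe and effective anticoagulation, and for that age has to be separated from clinical risk.

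**Working it through.** The plan states no score mean, SD, sample size or power, so there is no figure to reproduce. The check works out the built-in gap and then how often a test would flag it.

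**Inputs from the documents**
- Groups 70-79, 80-89 and 90+ (SAP); entry from age 70 (protocol 4.1).
- Equal numbers per decade intended, none stated (protocol 4.3).
- Significance at 0.05 (SAP); two-sided is assumed because the SAP does not say.

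**Assumptions, none given in the documents**
- Scoring: 1 age point at 65-74, 2 age points from 75, 1 point for female sex.
- p, the share of the 70-79 group aged 70-74: between 0 and 1, with 0.5 as the worked case.
- SD of the total score: 1.2 to 1.5.
- n per decade: 30, 50 or 100.

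**Step 1: mean age points per decade**
- 70-79: 1 × p + 2 × (1 − p) = 2 − p
- 80-89: 2
- 90+: 2

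**Step 2: built-in gap when all clinical items are identical**
- 70-79 versus 80-89: 2 − (2 − p) = p
- 70-79 versus 90+: 2 − (2 − p) = p
- 80-89 versus 90+: 2 − 2 = 0

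The gap is 0.25 points at p = 0.25, 0.50 at p = 0.50 and 0.75 at p = 0.75. With the age points removed it is 0 for every pair.

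**Step 3: chance that the gap alone gives P < .05**

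For two groups of n, in the normal approximation, power ≈ Φ(gap / (SD × √(2/n)) − 1.96). At p = 0.5, so a gap of 0.5:

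| n per decade | SD 1.5 | SD 1.2 |
|---|---|---|
| 30 | Φ(1.291 − 1.96) = 25% | Φ(1.614 − 1.96) = 36% |
| 50 | Φ(1.667 − 1.96) = 38% | Φ(2.083 − 1.96) = 55% |
| 100 | Φ(2.357 − 1.96) = 65% | Φ(2.946 − 1.96) = 84% |

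The noncentral t gives values at most 1 percentage point lower. At n = 100 and SD 1.5, p = 0.25 gives 22% and p = 0.75 gives 94%. The result therefore depends heavily on both p and n.

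**Step 4: the sex point**

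The contribution is the difference in female share × 1 point. A difference of 10 to 20 percentage points, assumed for illustration, adds 0.1 to 0.2 points. It comes from the sex mix of the groups, not from the age grouping.

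**The case against.** The strongest reply is that the score is doing its job. Protocol section 5.4 presents a validated stroke-risk tool, and such a tool counts age because age is a stroke risk factor. A higher total in older patients is then a correct statement of predicted risk. It misleads only if read as a difference in clinical disease, and neither document says it will be read that way. This stands as a reason to keep the full score. It does not make a test between age groups informative, since part of the result is fixed by how the groups were formed.

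Second, the SAP names the score only as a descriptive characteristic, and its sentence on tests does not mention the score. A t test on the total is thus a possible reading, not an explicit plan. This stands in part: section 6 does call for a comparison, and the SAP's sentence on tests is not limited to outcomes.

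Third, the point weights and all the numerical inputs are assumptions. That is so, and the sample size matters most. The size can be given only as a range.

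A reader might also infer three stronger claims, which the documents do not support:
- That every difference between decades is contaminated. Under the assumed scoring, 80-89 versus 90+ has no age-point gap, and this contrast is the closest to the study's question about the very old.
- That the sex point is also age compared with itself. It matters only if the sex mix differs by decade, and sex is compared separately in section 6.
- That the outcome analyses are biased. No listed outcome is computed from the score or adjusted for it.

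**Conclusion.** The concern holds in a limited form and is minor. Section 6 compares a score that includes age between groups defined by age, with no age-free version beside it. Two of the three pairwise contrasts, those involving 70-79, contain a gap of p points that says nothing about clinical risk factors. It cannot exceed 1 point and is 0.5 if half of that group is under 75. At that value a t test on the total would flag the gap alone somewhere between 25% and 84% of the time, for 30 to 100 patients per decade and an SD of 1.2 to 1.5.

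This rests on the usual age scoring, which the documents do not reproduce, and on assumed values of p, SD and n. It would be wrong to conclude that the primary or secondary results are invalid, or that the full score should be dropped. What suffers is the interpretation of the only listed stroke-risk summary when stroke by decade is read against it.

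**What to change.** In protocol section 6 and in the SAP, make the between-decade comparison on the enrollment CHA2DS2-VASc sum without its age points. The sex point may also be left out, since sex is compared separately. Show the full score beside it as description, without a test between decades, and label it as including up to 1 point of age difference in contrasts with 70-79. State the scoring in the SAP so that the reader can see what was removed.

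The cost is a few lines of wording. The age points follow from each subject's age when the score was taken and can be subtracted from the total, so no new data are needed.
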